1.1. Summary of Design

This is a multi-centre open-label randomized controlled trial in which recruited patients will be randomized in a 2:1 ratio to receive either 500 mL of COVID-19 convalescent plasma (CCP) comprised of a 500 mL unit from one donor or two 250 mL units from one or two donors collected by apheresis, or standard of care. The plan is to randomize 1200 individuals to obtain an expected 800 patients in the CCP arm and 400 patients in the arm receiving standard of care.

1.2. Primary Study Objectives

The primary objective is to determine the effect of COVID-19 convalescent plasma (CCP) on the risk of intubation or death at Day 30 in adult patients hospitalized for COVID-19 respiratory illness.

1.3. Sample Size Justification

Assuming a 30% risk of the composite outcome of intubation or death by Day 30 among hospitalized patients under standard of care, a sample size of 1200 individuals (800 in the CCP arm, and 400 in the standard of care arm) will provide 80% power ($\beta = 0.20$) to detect a relative risk reduction of 25% with CCP therapy using a 2-tailed test at level $\alpha = 0.05$. We assume that no patient will be lost to follow-up.

2. Responses

2.1. Primary Outcome

The primary outcome is intubation or death at Day 30 (the date of randomization being Day 1).

2.2. Secondary Outcomes

2.2.1. Time to intubation or death

The number of days from randomization to the first event of intubation or in-hospital death will be recorded. The censoring time for individuals not receiving intubation or dying will be the minimum of i. the number of days from randomization to discharge, and ii. Day 30. The 30-day limit is specified to align with the time horizon of the primary outcome.

2.2.2. Ventilator-free days

The number of ventilator-free days between randomization and Day 30 will be computed as the number of days during this 30-day period of time during which they were alive and not requiring ventilation. This total number of days could be made up days prior to ventilation and the number of days after discontinuation of ventilation if ventilation is required. Patients will be contacted at Day 30 by telephone to determine whether there were any ICU admissions since discharge from the hospital they were in at the time of recruitment. Patients discharged from hospital will be assumed to be off-ventilator post-discharge unless otherwise indicated.

2.2.3. In-hospital death by Day 90

This response will be a binary indicator of whether a patient died in-hospital within 90 days of randomization.

2.2.4. Time to in-hospital death

The number of days from randomization to in-hospital death will be recorded. The censoring time for individuals not dying in hospital will be the minimum of i. the number of days from randomization to discharge, and ii. to Day 90. The 90-day limit is specified to be large enough that it is highly unlikely to be the factor leading to censoring, but is small enough that it will mitigate the need to follow individuals who are hospitalized for an unusually long time until they are discharged.

2.2.5. Death by Day 30

This response is a simple binary indicator indicating whether the patient has died between randomization and Day 30.

2.2.6. Length of stay in intensive care unit

The number of days spent in the intensive care unit (ICU) over the 30-day period following randomization will be recorded. This total number of ICU days could be made up days from multiple admissions within the 30-day period from randomization if they are discharged and re-admitted a second time within this 30-day period. Patients will be contacted at Day 30 by telephone to determine whether there were any hospital admissions since discharge from the hospital they were in at the time of recruitment. Patients discharged from hospital will be assumed not to be in an ICU elsewhere, unless otherwise indicated.

2.2.7. Length of stay in hospital

The number of days from randomization to the first event of death or discharge will be recorded as the length of stay in hospital. This time will be right-censored at 90 days to avoid the need to follow individuals who are hospitalized for a particularly long time until discharge; it is expected that most hospitalizations will not last beyond 90 days.

2.2.8. Need for Extra-Corporeal Membrane Oxygenation (ECMO)

This response will be a binary indicator indicating whether the patient required extra-corporeal membrane oxygenation during the 30-day period following randomization.

2.2.9. Need for renal replacement therapy

This response will be the binary variable indicating that the patient required renal replacement therapy during the 30-day period following randomization.

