4.1.2. Exclusion Criteria

- 1. Onset of signs or symptoms of COVID-19 respiratory illness >12 days prior to randomization (eg. cough, chest pain, dyspnea, or hypoxia)
- 2. Intubated or plan in place for intubation
- 3. Plasma is contraindicated (e.g. history of anaphylaxis from transfusion)
- 4. Decision in place for no active treatment

Potential patients will be approached for informed consent. After consent is obtained, a screening ABO blood group will be collected if not already performed during the current hospital admission. Co-enrolment in other trials is allowed. For patients who fail screening, we will collect only the reason for screen failure with no personal identifiers.

Pregnant patients will not be excluded from the study if they meet eligibility criteria, except for sites where pregnant patients are not permitted to participate in the research as per local regulatory requirements. While young adults and pregnant women have been infrequently reported to present with complications, data from current COVID-19 wards indicate that those who develop severe COVID-19 pneumonia appear to have a similar risk of progression to intubation and critical disease than older patients. At the CHUM in Montreal, over half of COVID-19 patients admitted to the ICU were younger than 55 years of age. From a safety standpoint, CCP was well tolerated in one pregnant patient in a case series reported from China²¹. Therefore, based on current eligibility criteria, the same risk/benefit considerations apply to pregnant and younger patients as compared to the elderly, hence the reason not to exclude them from this trial.

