8.3. Collection of daily hospital data

Baseline data will be collected on Day 1 (see Section 8.5).

During the index hospital admission, daily data will be collected until discharge or Day 30 from randomization, whichever comes first. For enrolled patients who are still in hospital beyond Day 30, the date of discharge or death will be recorded up until Day 90 at which point data collection will be censored. This information will be obtained by reviewing the medical chart, by telephone follow-up or, if feasible through, provincial/state or national databases.

If the patient has routine blood drawn for laboratory testing pre-randomization and between 24 hours and 5 days (sample closest to 48 hours will be selected in preference) post-randomization, the discard plasma/serum from that sample will be retrieved, aliquoted and frozen for future testing. Alternatively, an extra tube can be added to the routine blood draw for research.

A Schedule of Assessment Events is available below for reference.

Schedule of Assessment Events

			Follow up		
Visit	Screening	Baseline (D1)	D2 - D30 ⁽¹⁾ (or until discharge)	D30 ⁽²⁾ (if patients discharged)	D90
Time Window (days)				+/- 3	+/- 7 days
Informed Consent/Assent	Х				
Verify Eligibility Criteria	X				
Randomization		Х			
CCP Administration (3)		Х			
Demographics		Х			
Co-morbidities		Х			
COVID-19 History ⁽⁴⁾		Х			
Height and Weight		Х			
Vital Signs		Х			
SpO ₂		Х	Х		
FiO ₂		Х	X		
COVID treatments		Х	Х	Х	
Hospitalization Daily Assessment (5)		Х	X		
Results of blood tests (done as per		Х	X ⁽⁶⁾		
clinical need)					
EQ-5D-5L ⁽⁷⁾		Х		Х	
Vital Status (dead/ alive)			Х	Х	X
Adverse Event Review		Х	Х	Х	
Discharge status (8)				Х	
Mechanical Ventilation since discharge				Х	
Viral load, cytokines and anti-CoV-2 titers ⁽⁹⁾		Χ	Х		

⁽¹⁾ Only collected if still hospitalized

⁽²⁾ Phone call if subject is already discharged from the hospital

⁽³⁾ Only for subject randomized to the convalescent plasma treatment

⁽⁴⁾ Includes date of first symptoms; description of symptoms, and date of diagnostic test

⁽⁵⁾ Mechanical ventilation, ECMO, renal replacement therapy or myocarditis

⁽⁶⁾ Daily from Day 1-7, then Day 14 +/- 3 days

⁽⁷⁾ EQ-5D-5L to be collected on Day 1 after consent and prior to CCP administration and on Day 30 regardless of hospitalization status

⁽⁸⁾ Discharge or hospital status (admitted, home, local hospital, longterm care facility)

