12.4.2. Secondary Endpoints

A cause-specific Cox regression model will be fitted for the intubation-free survival time defined as the first of the times of intubation or death with censoring at discharge or 30 days whichever comes first. A hazard ratio and 95% confidence interval will be computed from this fitted model.

Cumulative incidence functions will be estimated and plotted for each treatment arm for the time to intubation or death.

The restricted mean number of ventilator-free days over the first 30 days will be compared between the two groups based on a nonparametric tests.

The time to in-hospital death will be analyzed using a cause-specific Cox regression model treating the minimum of the time of discharge and 90 days as the censoring time. A hazard ratio and 95% confidence interval will be computed from this fitted model. Cumulative incidence functions will be estimated and plotted to estimate the proportion of patients who died during the initial hospitalization up to 90 days from randomization.

Finally, the survival status of individuals will be recorded at day 30 and the proportion of individuals who have died will be computed for each arm with a two-sample Wald test carried out based on the proportions.

Length of hospitalization over 90 days and length of stay in the ICU over 30 days will be modeled using a Cox regression without any distinction between reasons for discharge.

The proportion of patients needing ECMO over 30 days will be compared between the two arms based on a two-sided test of the difference between proportions.

The proportion of patients needing renal replacement therapy over the first 30 days will be compared between the two arms based on a Wald test.

The proportion of patients developing myocarditis over the first 30 days will be compared between the two arms based on a Wald test.

The change in EQ-5D-5L utility value from baseline will be compared between the two arms.

Incremental cost per quality-adjusted life year between the CCP and standard care over the 30-day time horizon.

No multiplicity adjustments will be implemented for the secondary analyses. Procedures for addressing missing data will be described in the SAP.

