3.1. Intention to Treat Sample

The intention to treat (ITT) sample will be comprised of all patients who were randomized irrespective of whether they received the randomized intervention. That is, individuals randomized to the CCP arm who did not receive CCP would have their outcomes attributed to the CCP arm. Given the simple nature of the primary outcome we anticipate a very low rate of missing primary outcome data.

The primary analysis will be based on individuals with available outcome data and this is expected to be all patients given the simple nature of the primary outcome. For some secondary outcomes if an outcome is unknown for some individuals, analyses will be first

carried out for those with complete data (i.e. in a complete case analysis) based on a modified intention to treat sample (i.e. the intention to treat sample excluding those individuals with unknown outcome). Multiple imputation will be carried out for a sensitivity analysis in which outcome data will be generated for those where it is missing in order to approximate a true intention to treat analysis. For details of the multiple imputation procedure see Section 4.1.

3.2.Per Protocol Sample

The per protocol sample will be comprised of eligible individuals who are randomized and are treated according to the protocol. In this trial, patients will be excluded from the per protocol analysis if any of the following protocol violations occur:

- Received less than two units of CCP*
- Transfusion of second unit of CCP completed > 24 hours after randomization*
- Patient randomized to SOC but receives CCP
- Patient was randomized despite being ineligible for the trial

*special consideration will be given for instances where 1 x 500 mL unit was given

3.3.Safety Sample

The safety sample will be comprised of all randomized individuals and so will coincide with the intention to treat sample.

4. Statistical Analysis

In what follows, the analysis plans are described for the sample representing the intention to treat population. Similar analyses will be carried out for the modified intention to treat and per protocol samples.

4.1.Handling of Incomplete Data

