4.3.9. Need for renal replacement therapy

The probability of requiring renal replacement therapy between randomization and Day 30 will be estimated for each treatment group by the proportion of individuals randomized to each group requiring renal replacement therapy between randomization and Day 30. The primary analysis will be based on a 2-sided Wald test of the null hypothesis that the probability of requiring renal replacement therapy is the same among individuals receiving CCP or standard of care. The percent relative risk reduction will be estimated along with a 95% confidence interval.

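### The renal replacement outcome counts any therapy within 30 days, so patients already on maintenance dialysis would be near-certain events in both arms and would attenuate the reported relative risk reduction

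*SAP*

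**What the plan says.** SAP 2.2.9 defines the outcome: "This response will be the binary variable indicating that the patient required renal replacement therapy during the 30-day period following randomization". Nothing restricts it to therapy that began after randomization.

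Under SAP 4.3.9 the probability is "estimated for each treatment group by the proportion of individuals randomized to each group requiring renal replacement therapy between randomization and Day 30". The arms are compared with a two-sided Wald test, and "The percent relative risk reduction will be estimated along with a 95% confidence interval". Protocol 12.4.2 has the same comparison: "The proportion of patients needing renal replacement therapy over the first 30 days will be compared between the two arms". The analysis set is everyone randomized (SAP 3.1): "The intention to treat (ITT) sample will be comprised of all patients who were randomized irrespective of whether they received the randomized intervention".

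Protocol 4.1.1 and 4.1.2 contain nothing on renal function. The four exclusions are symptom onset more than 12 days before randomization, intubation or a plan for it, a contraindication to plasma, and "Decision in place for no active treatment".

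On baseline data, the schedule in Protocol 8.3 marks the daily hospital assessment at Day 1 as well as Days 2-30. Its footnote 5 lists the content as "Mechanical ventilation, ECMO, renal replacement therapy or myocarditis". The itemised Day 1 list in Protocol 8.4 includes co-morbidities but has no RRT entry. RRT first appears by name in Protocol 8.5, from Day 2 on.

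**The concern.** A patient on maintenance dialysis needs RRT within days of randomization whether or not plasma does anything for the kidney. As the outcome is worded, that patient enters the numerator as an event. The outcome then adds together two things: dialysis dependence brought into the trial, and kidney failure that arose in it. Only the second can respond to treatment.

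The effect measure is relative, so a block of events common to both arms shrinks it by construction. A reader of the final report could not tell a weak renal effect from a diluted one, because the plan does not ask for the number on dialysis at entry to be reported.

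**Working it through.** **The plan's own figure.** The only design calculation in the documents is for the primary composite: 30% against 22.5% (a 25% reduction), 800:400, two-sided 0.05. With pooled variance under the null this gives power 0.801 and a total of 1200, matching the stated 80%. It does not bear on RRT, for which the documents state no rate, effect or power.

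**Inputs.** From the documents: 800 CCP and 400 standard of care, all randomized patients analysed, Wald test, relative risk reduction reported. Assumed, because the documents are silent: q, the share on maintenance dialysis at entry, 1-4%; r, the risk of new RRT in the other controls, 3-6%; true relative risk for new RRT, RR = 0.75 or 0.60. Every patient on dialysis at entry is taken to be an event.

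**Model.** Control = q + (1−q)r. CCP = q + (1−q)r·RR. Reported relative risk = CCP/control.

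| q | r | Control | CCP at RR 0.75 | Reported RR (true 0.75) | Reported RR (true 0.60) | Share of control events present at entry |
|---|---|---|---|---|---|---|
| 1% | 6% | 0.0694 | 0.0546 | 0.786 | 0.658 | 14% |
| 1% | 3% | 0.0397 | 0.0323 | 0.813 | 0.701 | 25% |
| 4% | 6% | 0.0976 | 0.0832 | 0.852 | 0.764 | 41% |
| 4% | 3% | 0.0688 | 0.0616 | 0.895 | 0.833 | 58% |

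As an example, the last row has control 0.04 + 0.96×0.03 = 0.0688 and CCP 0.04 + 0.96×0.03×0.75 = 0.0616, a ratio of 0.895. A true 25% reduction would be reported as 10.5%. At q = 0 the reported value equals the true one.

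**Risk difference.** This is only multiplied by (1−q). At r = 5%, RR = 0.75 and q = 5% it moves from 0.0125 to 0.0119. The attenuation falls on the relative measure.

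**Power, unpooled Wald, q = 2%, r = 6%, RR = 0.60.**
- As defined: 0.0788 against 0.0553, difference 0.0235. SE = √(0.0788×0.9212/400 + 0.0553×0.9447/800) = 0.0157. Power = Φ(0.0235/0.0157 − 1.96), about 32%.
- New RRT only, 392:784: 0.060 against 0.036, difference 0.024. SE = √(0.060×0.940/392 + 0.036×0.964/784) = 0.0137. Power is about 42%.

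**Power, pooled variance, q = 2%, r = 5%.** At RR = 0.75, 13.8% as defined and 18.2% for new RRT only. At RR = 0.50, 43.7% and 60.3%.

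**Can Day 1 data identify these patients?** SAP 2.1 makes the randomization date Day 1, and Protocol 8.4 places the Day 1 procedures after randomization. A Day 1 RRT record could therefore reflect therapy begun after randomization. Dialysis is also intermittent, so a patient not dialysed that day would look free of RRT. The Day 1 record alone can err in both directions.

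**The case against.** The strongest reply has four parts.

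*The size is assumed.* This stands. Neither the prevalence of dialysis at entry nor the new-RRT rate is in the documents. SAP 4.1 names kidney disease only as an example of a co-morbidity for the imputation model, which does not show that dialysis patients are expected. The 14-58% share of control events reflects the chosen inputs and is not a forecast.

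*The comparison remains valid.* This also stands. A reader might infer bias in favour of one arm, or that a chance imbalance in dialysis patients could pass for a treatment effect. The documents do not support that reading. Randomization balances these patients on average, the test keeps its type I error, and chance imbalance is ordinary sampling error already covered by the confidence interval.

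*The wording may be a drafting template.* Myocarditis (SAP 2.2.10) is phrased as something that developed after randomization, but ECMO (SAP 2.2.8) shares the RRT phrasing. The contrast therefore does not prove a decision to count maintenance dialysis. The rule as written counts it nevertheless.

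*Analysing everyone randomized is the stated principle.* That is true, but restricting on status fixed before randomization preserves the randomized comparison, provided the status is established without using post-randomization data.

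Calling these patients automatic events would also go too far. Protocol 8.5 records RRT only until discharge, death or Day 30, and the Day 30 items in Protocol 8.8 do not ask about it. A patient who dies or leaves early may have no recorded session.

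**Conclusion.** The definition mixes dialysis present at entry with new kidney failure, and nothing in either document separates them. Under the assumed rates, a true relative risk of 0.75 would be reported as about 0.79-0.90, and a true 0.60 as about 0.66-0.83. If no dialysis patient is enrolled, the effect is nil.

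The consequence is attenuation and lost power for one of 15 secondary outcomes, analysed without multiplicity adjustment. The primary analysis, the sample size and the stopping rule are untouched. At a true relative risk of 0.75 this outcome has little power under either definition, so the gain from the change is mainly in what the estimate means. The wording gap is certain; its size in this trial cannot be known from the documents.

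A reader might also infer that the scheduled Day 1 RRT entry makes this a matter of SAP wording alone. The documents do not support that, because Protocol 8.3 and 8.4 disagree on whether RRT is a Day 1 item, and a Day 1 entry does not by itself establish status before randomization.

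**What to change.** In SAP 2.2.9, SAP 4.3.9 and Protocol 12.4.2, define the outcome as new RRT started after randomization and by Day 30, among patients who were not on chronic dialysis and had not started RRT before randomization.

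- Establish that status from the baseline co-morbidity and medical chart data together with the Day 1 assessment, not from whether a session was recorded on Day 1.
- Align the baseline list in Protocol 8.4 with the Day 1 RRT entry in the Protocol 8.3 schedule.
- Report the number excluded for this reason by arm.
- Keep the any-RRT analysis in all randomized patients as a sensitivity analysis.

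The cost is a slightly smaller denominator for this one outcome. If the co-morbidity form, whose content the documents do not show, does not already capture chronic dialysis, one chart-derived baseline item is also needed. No extra visit or sample is required.

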2.2.10. Myocarditis

This binary response will indicate whether the patient developed myocarditis (as defined by the medical team) between randomization and Day 30.

2.2.11. Patient-reported outcomes (PROs)

PRO will be measured using a widely used generic instrument called EQ-5D-5L. It measures health-related quality of life in five dimensions, namely, mobility, self-care, usual activities, pain/discomfort, and anxiety/depression. Patients can report five level impairment, reflecting no, slight, moderate, severe, and extreme problems in each dimension. The EQ-5D-5L will be administered at baseline and Day 30.

2.2.12. Incremental cost per quality-adjusted life year (QALY)

A cost effectiveness analysis alongside the trial will be conducted. The summary measure for the economic evaluation is incremental cost per QALY comparing CCP with standard care over the 30-day trial period.

2.3. Adverse Events

2.3.1. Adverse event reporting

The severity of each AE will be assessed by the Investigator and graded based on the Common Terminology Criteria for Adverse Events (CTCAE) version 4.0. Adverse events graded as 1 or 2 require no further documentation, unless they are related or probably related to CCP. Adverse events graded as 3, 4 and 5 must be reported on the eCRF within 7 day and are categorized as expected or unexpected. Serious adverse events (SAEs) deemed to be unexpected and related to or probably related to the investigational products must be reported to the sponsor within 24 hours. All other SAEs must be reported to the sponsor within 96 hours (Protocol section 9).

